
Criteria for Determination of Dose-Limiting Toxicity (Part 1):
	
Dose-limiting toxicities will be determined during the first cycle (four weeks/ 28 days) of treatment. A DLT is defined by the occurrence of any of the following toxicities related to ARQ 087 within the first cycle of treatment and graded according to the Common Terminology Criteria for Adverse Events (CTCAE) version 4.03:
 
 
• Grade 4 anemia
 
• Grade 4 neutropenia
 
• Grade 4 thrombocytopenia
 
• Grade 3 neutropenia with fever (<math>\geq 38^{\circ}\text{C}/100.4^{\circ}\text{F}</math>)
 
• Grade 3 neutropenia lasting longer than 7 days despite optimal treatment
 
• Grade 3 thrombocytopenia in the presence of bleeding
 
• <math>\geq</math> Grade 3 hyperglycemia (fasting blood glucose <math>> 250</math> mg/dL or non-fasting <math>> 500</math> mg/dL) requiring insulin (uncontrolled with metformin)
 
• <math>\geq</math> Grade 3 non-hematological toxicity of any duration, except for the following: 
 
○ Nausea, vomiting, or diarrhea responding to optimal medical management within 48 hours
 
○ Alopecia
 
 
 
• Any other toxicity that in the view of the Investigator represents a clinically significant hazard to the subject
 

Statistical Methods:	
All subjects receiving at least one daily dose of ARQ 087 will be considered evaluable for safety analyses. In addition to the evaluation and categorization of adverse events, listings of laboratory test results collected at baseline and during the study will be generated. Descriptive statistics summarizing the changes in those laboratory tests over time will be presented.
 
Subjects who have received at least one cycle of ARQ 087 and have had at least one disease assessment following the initiation of therapy will be considered evaluable for response. The anti-tumor activity will be evaluated on an exploratory basis and will be summarized using descriptive statistics or graphics.
 
For the Expanded Cohort (Part 2), for the iCCA sub-cohort, statistical analysis will include interim monitoring for futility. After response data from 10 subjects with iCCA are available, the response rate will be assessed. If the objective response is observed in <math>\leq 30\%</math> of enrolled subjects, the enrollment will be stopped for lack of efficacy.

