### **Cohort 5 and all Subsequent Dose Escalation/Food-effect Cohorts (Part 1)**

Tumor assessments (CT scan, MRI, or PET scan) will be performed at Baseline, and every eight weeks during Treatment Period 2 (e.g., on Day 1 of every odd cycle, Cycle 3 Day 1, Cycle 5 Day 1, or Week 8, Week 16, etc.) or as otherwise clinically indicated.

Dose escalation will be performed after three or six subjects are evaluated in each cohort (see Table 4.1). If a DLT is observed in one of the three subjects in a cohort in the first 28 days of therapy, the additional three subjects will be enrolled in the cohort sequentially.

If no DLT is seen in the first three evaluable subjects in the first 28 days of therapy, dose escalation will occur and another three subjects will be enrolled and treated at the next ARQ 087 dose level. If two or more subjects experience a DLT at Dose Level 1, subsequent subjects will be enrolled at a lower dose or at a less frequent drug administration schedule (e.g., 25 mg twice a week). If a subject withdraws from study treatment for any reason other than a DLT during the first 28 days (first cycle), that subject will be replaced.

The MTD is defined as the dose level at which no more than one subject with a DLT is observed among six subjects. Once the MTD is determined, up to six additional subjects may be treated at this dose level of ARQ 087. If the MTD is not reached, dose escalation will proceed with the purpose of determining a RP2D of ARQ 087.

In the first four cohorts, the dose may be doubled, and in the next cohorts, the dose escalation will follow a modified Fibonacci scheme (increase by 50%, 30%, and 25%) until RP2D or MTD is determined.

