#### 4.5 Dose-Limiting Toxicity

Dose-limiting toxicities will be determined during the first four weeks/28 days (first cycle) of Treatment Period 2 (Cohorts 1-4) or during Cycle 1 (Cohort 5 and all subsequent cohorts). A DLT is defined by the occurrence of any of the following toxicities related to ARQ 087 within the first 28 days of continuous treatment (Treatment Period 2 or Cycle 1 of Continuous Dosing) and graded according to the Common Terminology Criteria for Adverse Events (CTCAE) version 4.03:

- Grade 4 anemia
- Grade 4 neutropenia
- Grade 4 thrombocytopenia
- Grade 3 neutropenia with fever ( $\geq 38^{\circ}\text{C}/100.4^{\circ}\text{F}$ )
- Grade 3 neutropenia lasting longer than 7 days despite optimal treatment
- Grade 3 thrombocytopenia in the presence of bleeding
- $\geq$  Grade 3 hyperglycemia (fasting blood glucose  $> 250$  mg/dL or non-fasting  $> 500$  mg/dL) requiring insulin (uncontrolled with metformin)
- $\geq$  Grade 3 non-hematological toxicity of any duration, except for the following:
  - Nausea, vomiting, or diarrhea responding to optimal medical management within 48 hours
  - Alopecia
- Any other toxicity that in the view of the Investigator represents a clinically significant hazard to the subject

**Note:** During the dose escalation phase, if the subject experienced a DLT, such subject should be permanently discontinued from the treatment.

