## 6.5 Pharmacokinetic Assessments

Pharmacokinetic variables will include  $C_{max}$ , AUC, and half-life. To assess single dose PK, blood samples will be collected for four consecutive days during Treatment Period 1 (Cohorts 1-4), on Day 1 (full assessment), Day 2 (24 hrs post-dose), Day 3 (48 hrs post-dose), and Day 4 (72 hrs post-dose). The washout period between Treatment Period 1, Day 1 and Treatment Period 2, Day 1 Cycle 1 should be at least 72 hours. During Treatment Period 2 (continuous administration of ARQ 087), PK samples will be collected on Day 8, Day 15, Day 22 (full assessment), and Day 23 (24 hrs post-dose on Day 22) of Cycle 1 (see Appendix 3). However, for subjects enrolled in **Cohort 1** (25 mg every other day), Cycle 1 Week 4 visits should be scheduled on the day of ARQ 087 administration and the next consecutive day, when drug is not taken, e.g., Cycle 1 Day 21 and Day 22 or Cycle 1 Day 23 and Day 24. Also, a Cycle 1 Day 1 pre-dose sample should be collected if the Cycle 1 Day 1 visit differs from the Treatment Period 1, Day 4 visit (72 hours).

During continuous administration of ARQ 087 (Cohort 5 and all subsequent cohorts, including ALL subjects enrolled in the Food-effect Cohort, and for up to 10 subjects enrolled in the Expanded Cohort at selected sites), PK samples will be collected on Day 1 (full assessment), Day 2, Day 8 (pre-dose), Day 15 (pre-dose), Day 22 (full assessment), and

Day 23 (pre-dose) of Cycle 1; and on Day 1 and Day 15 of all subsequent cycles (pre-dose), and End of Treatment (see Appendix 3).

The blood sampling date and time and the time of the last dose of ARQ 087 administration prior to PK blood draw should be recorded on the eCRF.

Detailed instructions for collection and shipment of plasma PK samples will be provided in the laboratory manual.

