5.2 General Statistical Considerations

All summary tables will include all subjects from cohort 1 to the last cohort enrolled and be presented by treatment groups, including low dose group (25 mg QOD – 200 mg QD), middle dose group (250 mg QD – 325 mg QD), high dose group (400 mg QD - 425 mg QD), expanded (RP2D) cohort (300 mg QD) and Overall.

Categorical variables will be summarized as the number and percentage of subjects in each category. Continuous variables will be summarized as mean, standard deviation, median, minimum and maximum.

As appropriate, all data collected on the electronic case report form (eCRF) will be presented in listings. All statistical analyses will be performed using SAS® version 9.2 or higher.

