5.4.7 Analyses of Safety Variables

All analyses for the safety variables will be performed on safety population. Safety variables include adverse events, laboratory parameters, vital signs, ECOG performance status, 12-lead ECG and physical exams.

Descriptive statistics will be calculated for quantitative safety data, frequency counts and percentages will be compiled for classification of qualitative safety data. All percentages will be calculated based on the number of subjects in the safety population, unless otherwise indicated. Baseline is defined as the last non-missing value prior to the first dose date or on day 1, unless otherwise noted.

Adverse Events

Adverse events will be evaluated for severity using NCI-CTCAE, version 4.03. AE summaries will include treatment-emergent adverse events (TEAEs).

A TEAE is defined as:

- an AE which is not present prior to the first dose of ARQ 087 and started after taking the study drug during the treatment period or within 30 days after the last dose of the study drug;
- an AE which is present prior to the first dose of ARQ 087 and increased in severity after taking study drug during the treatment period or within 30 days after the last dose of study drug;
- an AE which is considered study drug-related regardless of the start date of the event.

All TEAEs will be coded using Medical Dictionary for Regulatory Activities (MedDRA[®]) Version 15.1 and summaries will be presented by system organ class and preferred term. Separate TEAE summaries will be generated for the following categories:

- All TEAEs
- Severe TEAEs (Grade 3 or higher)
- SAEs
- TEAEs related to study drug
- TEAEs leading to treatment discontinuation
- TEAEs leading to treatment interruption
- TEAEs leading to treatment interruption then dose reduction
- TEAEs resulting in death
- TEAEs listed according to maximum severity
- TEAEs classified as DLTs

TEAEs will be summarized by presenting the number and percentage of subjects having at least one TEAE in each system organ class and preferred term. A subject with multiple occurrences of the same TEAE will be counted only once in the AE category.

Separate TEAE summaries will be presented by system organ class, preferred term, and maximum CTCAE 4.03 grade. A subject with multiple CTCAE grades for the same TEAE will be summarized under the maximum CTCAE grade recorded for the event.

Laboratory Test

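### The documents conflict on whether DLTs are classified in the Expanded Cohort, yet the SAP tabulates DLTs for that cohort and Overall

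*SAP*

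**What the plan says.** **Which cohorts are assessed for DLTs**

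- Protocol synopsis: the criteria stand under the heading "Criteria for Determination of Dose-Limiting Toxicity (Part 1").
- Protocol Section 4.5: DLTs are determined in the first 28 days of Treatment Period 2 for Cohorts 1-4, "or during Cycle 1 (Cohort 5 and all subsequent cohorts"). No limit to Part 1 is stated.
- Protocol Section 4.5, closing note: permanent discontinuation after a DLT is introduced by "During the dose escalation phase, if the subject experienced a DLT".
- Protocol Section 7.3: the same discontinuation rule appears without that restriction.

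**What the SAP tabulates**

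- Section 5.4.7 requires a summary of "TEAEs classified as DLTs". It gives no DLT definition and no cohort restriction. Percentages use the safety population (any amount of drug, Section 4.2) unless otherwise indicated.
- Section 5.2 has all summary tables include all subjects, by low, middle and high dose group, "expanded (RP2D) cohort (300 mg QD) and Overall".
- Section 4 names four analysis populations. None is a DLT-evaluable population.
- Section 11 suppresses the percentage when a count is zero.

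**The concern.** A DLT count can be read only if the reader knows in whom DLTs were looked for. Under the synopsis heading, a related Grade 3 event in Cycle 1 at 250 or 325 mg in Part 1 may be a DLT, while the same event at 300 mg in Part 2 is never put to the question. Under Section 4.5 read broadly, both are classified. Sites could reasonably differ, and the planned table would show the result as if ascertainment were uniform.

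The comparison matters because safety and tolerability is the primary objective and further evaluation of the RP2D is a secondary one. Neither dosing table lists a Part 1 cohort at 300 mg, so the Expanded Cohort is the planned source of data at that dose. Its column would stand in the same table as the 250-325 mg group.

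The label may also carry a consequence for the subject. Section 7.3 ties discontinuation to a DLT without naming a phase, while Table 7.1 allows restart after some Grade 3-4 toxicity. These passages need to be reconciled; nothing is said here about which should prevail.

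**Working it through.** **1. Is the scope really unsettled?** The plan states no figure to reproduce, so the passages are set side by side.

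- For a broad reading: the synopsis section on test product and dose expressly includes the Expanded Cohort among the cohorts starting with Cohort 5. Section 6.4 applies the Section 4.5 phrase to laboratory timing and gives the Expanded Cohort no rule of its own. Where Part 1 alone is meant, the protocol can say so, as in the Section 4.1.1 subheading "Cohort 5 and all Subsequent Dose Escalation/Food-effect Cohorts (Part 1").
- For a narrow reading: the synopsis section on pharmacokinetic and pharmacodynamic variables uses similar wording under a Part 1 label, then gives Part 2 a separate schedule. DLTs also serve the escalation rules, which belong to Part 1.
- Section 6.5 is weak evidence either way. After the phrase it adds "and for up to 10 subjects enrolled in the Expanded Cohort at selected sites", a separate clause that concerns PK sampling only.

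Usage is mixed, and no passage says which one governs.

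**2. Share of the Overall denominator not assessed, if Part 2 is out of scope**

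Inputs: SAP Table 1 has nine escalation cohorts of 3 to 6 subjects, at least 6 food-effect subjects (taken as 6), and about 50 to 60 Expanded subjects.

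- Part 1: 9 × 3 + 6 = 33 to 9 × 6 + 6 = 60.
- Lowest Expanded share: 50 / (60 + 50) = 45%.
- Highest Expanded share: 60 / (33 + 60) = 65%.
- With the ten numbered escalation cohorts of protocol Table 4.1, Part 1 is 36 to 66 and the share is 50/116 = 43% to 60/96 = 63%.

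**3. Dilution of the Overall percentage**

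With k DLTs in Part 1 and none classified in Part 2, the Part 1 rate is k/n₁ and the Overall rate is k/(n₁ + n₂). Their ratio, n₁/(n₁ + n₂), does not depend on k. It runs from 33/93 = 35% to 60/110 = 55%. The values k = 2 and k = 4 below are assumptions.

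| Part 1 | Expanded | DLTs | Part 1 rate | Overall rate |
|---|---|---|---|---|
| 33 | 50 | 2 | 6.1% | 2/83 = 2.4% |
| 33 | 50 | 4 | 12.1% | 4/83 = 4.8% |
| 33 | 60 | 2 | 6.1% | 2/93 = 2.2% |
| 33 | 60 | 4 | 12.1% | 4/93 = 4.3% |
| 60 | 50 | 2 | 3.3% | 2/110 = 1.8% |
| 60 | 50 | 4 | 6.7% | 4/110 = 3.6% |
| 60 | 60 | 2 | 3.3% | 2/120 = 1.7% |
| 60 | 60 | 4 | 6.7% | 4/120 = 3.3% |

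**4. Why a zero would be ambiguous.** If DLTs were assessed and the true rate were 10% (assumed), the chance of none would be 0.9⁵⁰ = 0.5% or 0.9⁶⁰ = 0.2%. An assessed zero would therefore be informative. An unassessed zero carries no information. The planned cell would look the same in both cases.

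**The case against.** The best case against the point has four parts.

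- *Part 1 is the natural reading.* DLTs drive escalation and the MTD, and the SAP defines the MTD under its Part 1 heading. This has force, but it does not remove the problem. If Part 1 governs, the SAP still prints an Expanded column and a pooled percentage for subjects never classified.
- *If Section 4.5 covers Part 2, there is no scope defect in the table.* Correct. The harm depends on Part 2 being unclassified or classified inconsistently.
- *Toxicity at 300 mg stays visible.* Also correct. Expanded Cohort adverse events are assessed on Days 1, 8, 15 and 22 of Cycle 1 and graded by CTCAE 4.03. The tables of Grade 3 or higher, related and serious TEAEs are shown by group, as are laboratory shifts. None of them applies the DLT criteria or the 28-day window, so they limit the damage without replacing the comparison.
- *No decision turns on it.* The RP2D is already set, no formal testing is planned, and no Part 2 rule uses a DLT rate. This stands and keeps the point at the level of reporting.

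The table shells are not in the text available, so a footnote or restriction there cannot be ruled out. The SAP text itself contains none.

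A reader might infer that the 300 mg column would report 0% because nobody looked, or that the RP2D would appear free of toxicity. The documents do not support this. A zero count prints without a percentage, no confidence limit is specified for TEAE tables, and the events themselves are collected and shown elsewhere.

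**Conclusion.** The point holds as a conditional reporting defect. The documents disagree on DLT scope, and the SAP tabulates DLTs as if the scope were uniform. If Part 2 is not classified, the Overall percentage falls to about 35% to 55% of the Part 1 rate. With an assumed 2 to 4 Part 1 DLTs, that means 1.7% to 4.8% Overall against 3.3% to 12.1% in Part 1. If sites differ, the Expanded cell is a partial count with no known denominator.

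The size rests on cohort sizes as planned in SAP Table 1, without replacement subjects or the additional subjects allowed at the MTD. A larger Part 1 would lessen the dilution. The DLT counts are illustrative. The existence of the conflict depends on none of these numbers.

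**What to change.** 1. **Protocol.** The sponsor should reconcile the synopsis heading, Section 4.5 and Section 7.3 on which cohorts are classified for DLTs and on the scope of the discontinuation rule. No clinical rule is proposed here.
2. **SAP Section 5.4.7.** Restrict the DLT table and its total column to the cohorts in which DLTs are classified, and mark any other column as not assessed. If Part 2 is in scope, state that and keep the columns.
3. **Optional.** Add a table for all groups of related events in the first 28 days of continuous dosing that meet the objective grade criteria of Section 4.5. Label it as not equivalent to prospectively classified DLTs, because several criteria (response to optimal management, control with metformin, investigator-judged hazard) would need judgement after the fact.

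The cost is a clarification in the protocol, a few lines in the SAP and the loss of one pooled figure if Part 2 is out of scope. The optional table adds some programming and manual review.

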### 6.4 Clinical Laboratory Tests

Safety laboratory determinations will include hematology, blood chemistry, liver function tests, coagulation tests, and urinalyses. All laboratory tests required during the study must be obtained at a local laboratory designated by the Investigator. Fasting clinical blood tests obtained during the Pre-study Visit can be used for Day 1 if they are performed within 72 hours prior to the first dose of the study drug (Treatment Period 1, Day 1 in Cohorts 1-4 or Cycle 1 Day 1 visit in Cohort 5 and all subsequent cohorts). During Treatment Period 2 (Cohorts 1-4) or the Continuous Treatment Administration (Cohort 5 and all subsequent cohorts), clinical blood tests can be obtained within 24 hours prior to the scheduled visit.

Chemistry samples should be taken in a fasting state (fasting at least 8 hours) prior to administration of the morning dose of ARQ 087\*.

- Hematology: complete blood count (CBC) including hemoglobin, hematocrit, white blood cell count (WBC) with 5-part differential, red blood cell (RBC), platelet, and reticulocyte count
- Blood chemistry: albumin, bicarbonate, blood urea nitrogen (BUN), calcium, chloride, creatinine, glucose, glycated hemoglobin (HbA1c)\*\*, magnesium, phosphate, potassium, total protein, sodium, uric acid
- Liver function tests (LFT): alanine transaminase (ALT), aspartate transaminase (AST), alkaline phosphatase (ALP), total and direct bilirubin, lactate dehydrogenase (LDH)
- Thyroid function tests (at Baseline and End of Treatment, and if clinically indicated): thyroid stimulating hormone (TSH), triiodothyronine (total T3), thyroxine (free T4)
- Coagulation tests (at Baseline and End of Treatment, and if clinically indicated): prothrombin time (PT), international normalized ratio (INR), and partial prothrombin time (PTT)
- Routine urinalysis: dipstick and microscopy (only if clinically indicated or dipstick is not done) including protein, specific gravity, glucose and blood
  - To assess ARQ 087 metabolism, the Sponsor may request collection of 24-hour urine samples
- Serum pregnancy test (at Baseline and End of Treatment only): for female subjects of childbearing potential

\*ARQ 087 should be administered in the fasted state, except to subjects enrolled in the Food-effect Cohort.

\*\*HbA1c should be done at Baseline and End of Treatment, and if clinically indicated

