Summary statistics for baseline, each post-baseline measurement, and change from baseline for each post-baseline measurement will be presented for all parameters in the safety population.

Toxicities will be graded according to the NCI CTCAE, Version 4.03. Shift table of toxicity grade for NCI CTCAE specified laboratory tests will also be presented in the safety population per treatment groups and overall.

Baseline is defined as the last non-missing value assessment made prior to the first dose of study medication, which is, for most subjects, the clinical laboratory assessment taken on Day 1 prior to the first dose. If it's missing, the laboratory assessment at screening (including pre-study visit and unscheduled visit) will be used as baseline value.

If lab results contain symbols like "<", ">", "≥" or "≤", extract the numeric value as the limit, Example: if result is ">0.1", "0.1" will be used for analysis.

Vital Signs

Summary statistics for baseline, each post-baseline measurement, and change from baseline for each post-baseline measurement will be presented for each vital sign parameter.

Individual absolute vital sign values and the change from baseline will be summarized descriptively for each treatment group and overall, by schedule of assessments.

ECOG Performance Status

Number and percentage of subjects having each ECOG performance status level will be presented for baseline and each post-baseline measurement, per treatment groups and overall.

In addition, the shift table comparing post baseline to baseline will also be presented per treatment groups and overall.

12-lead ECG

12-lead ECG absolute individual parameters [PR interval, QRS interval, QT interval, QTcF interval, QTcB interval and Summary (Mean) Ventricular Rate] and the change from baseline will be summarized per treatment groups and overall per assessment. All ECG measurements will be presented in the data listings.

Physical Examination

Data from physical examinations will be presented in the data listings as per subject per visit per body system, using safety population.

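### SAP 5.4.7 strips the sign from laboratory results without exempting CTCAE grading, so a result reported at a strict cut-off can appear one grade too low in the shift table

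*SAP*

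**What the plan says.** The Laboratory Test part of SAP 5.4.7 contains three instructions that meet at this point.

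- **Conversion.** When a result contains <, >, ≥ or ≤, the programmer is to "extract the numeric value as the limit". In the SAP's own illustration a result of '>0.1' becomes 0.1, and that number "will be used for analysis". No use is exempted.
- **Grading.** "Toxicities will be graded according to the NCI CTCAE, Version 4.03".
- **Output.** "Shift table of toxicity grade for NCI CTCAE specified laboratory tests will also be presented in the safety population". Separately, summary statistics and "change from baseline for each post-baseline measurement will be presented for all parameters in the safety population".

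The subsection has no rule for grading a signed result and no flag for one.

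Two places in the protocol matter. Section 6.4 says that "All laboratory tests required during the study must be obtained at a local laboratory designated by the Investigator", so reporting limits belong to each site's laboratory; neither document lists them. Section 4.5 (and the synopsis) describes hyperglycemia of Grade 3 or higher by strict inequalities: fasting glucose > 250 mg/dL, or non-fasting > 500 mg/dL.

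**The concern.** A '>x' result states that the true value is above x. Once the sign is removed, the analysed value is x itself. Where a grade begins strictly above x, the analysed value no longer qualifies for a grade that the reported result establishes. Results of the form '<x' mirror this for toxicities defined by low values.

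Safety and tolerability is the primary objective, and the laboratory shift table is one of its outputs. Glucose is a relevant analyte here. It has its own DLT criterion, protocol 1.6 reports transient increases in animals, and SAP 5.4.4 summarises it as a pharmacodynamic measure. The dose groups in SAP 3.1.1 are also small enough for one misplaced subject to be visible in a percentage.

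**Working it through.** The plan gives no figure of its own to reproduce, so the check applies the stated rule literally.

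**Inputs**

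- Conversion rule: '>L' is replaced by L (SAP 5.4.7).
- Strict cut-off: c = 250 mg/dL, fasting (protocol 4.5). Protocol 6.4 requires chemistry samples after a fast of at least 8 hours, and SAP 5.3 restricts analyses to scheduled visits apart from a fallback for baseline. The fasting limit is therefore the one that applies to the planned data.
- Reporting limit L: not given. Values from 200 to 600 mg/dL are assumed, to show the range.
- Assumption: the shift table uses the same fasting limit that the protocol attaches to Grade 3. The documents do not reproduce the CTCAE cut-offs.

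**Comparison**

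- Under the SAP rule, '>L' meets the cut-off only if L > c.
- The reported result guarantees a true value above the cut-off whenever L ≥ c.
- The two conditions differ at exactly one point, L = c.

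| Reported | Analysed value | Analysed value > 250? | True value > 250? | Sign kept for grading |
|---|---|---|---|---|
| '>200' | 200 | No | Possible, not known | Still undetermined; needs a flag |
| '>250' | 250 | **No** | **Certain** | Met |
| '>300' to '>600' | 300 to 600 | Yes | Certain | Met |

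There are therefore three cases at any strict cut-off:

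1. Reporting limit equal to the cut-off: the rule certainly under-grades.
2. Reporting limit on the milder side: under-grading is possible, but the grade cannot be settled under either approach.
3. Reporting limit beyond the cut-off: no error at that cut-off.

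For '<L' against a cut-off of the form < c, the same reasoning gives a certain error only at L = c. If a cut-off is inclusive (≥ c), stripping '>c' to c does no harm. A result written '≥L' or '≤L' already admits L.

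**Weight of one misgraded subject**

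This step is conditional on a misgrading occurring; it says nothing about how likely one is.

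- Middle Dose Group: the 250 mg and 325 mg cohorts, planned at 3 to 6 subjects each (SAP 2.2.1, Table 1), so 6 to 12 in all. One subject is 1/12 = 8.3% to 1/6 = 16.7%.
- Expanded Cohort: about 50 to 60 subjects. One subject is 1/60 = 1.7% to 1/50 = 2.0%.

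**The case against.** The best defence is that the SAP states a numeric convention and never says that grades are computed from the stripped number. That is true. However, the rule covers analysis without exception and sits in the same subsection as the shift table, so a programmer following the text would have no instruction to do otherwise. The defence supports treating this as a clarification; it does not remove the gap.

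A second objection is that the 250 mg/dL limit comes from a DLT definition, which also carries the qualifier "requiring insulin (uncontrolled with metformin", and that the shift table uses CTCAE cut-offs that the documents do not reproduce. This stands as a limit on what can be shown. The glucose figure demonstrates the mechanism at a cut-off that the protocol itself ties to a grade; it is not a survey of the table.

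Third, the safety assessment has other supports. Investigators review laboratory results and grade adverse events (protocol 8.2, 8.3 and 8.6). SAP 5.4.7 separately summarises Grade 3 or higher events, maximum grade and DLTs. Listings under SAP 5.2 can still show the result as reported. All of this stands, and it confines the problem to the laboratory tables. Listings do not, however, correct a count in a summary table.

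A reader might infer more than the documents support:

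- **That the rule always pulls the worst values toward normal.** Many signed results are clinically harmless, such as a low-end '<' for a test whose toxicity is defined by high values. A signed baseline can also be under-graded, which makes a shift look larger.
- **That the non-fasting limit of 500 mg/dL shows the failure.** Planned samples are fasting, and a result of '>500' becomes 500, which still exceeds 250.
- **That change from baseline is understated by a definable amount.** No figure in the documents allows that calculation, a signed baseline can act in the opposite direction, and using the limit in descriptive statistics is a workable convention if it is disclosed.
- **That DLT decisions are affected.** Nothing describes DLTs as derived from stripped numbers.

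**Conclusion.** The point holds for grading only, and it is minor. As written, the rule permits a result to be placed on the less severe side of a limit that it is known to exceed, one grade below what the reported result establishes. This is certain where a reporting limit coincides with a strict cut-off. It is possible but unresolvable where the reporting limit lies on the milder side, and it does not occur at a cut-off that the reporting limit lies beyond.

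The conclusion rests on two assumptions: that grades are derived from the converted number, which the SAP's unrestricted wording implies but does not state, and that at least one local reporting limit coincides with a strict cut-off. The documents give no reporting limits, so the number of affected results cannot be estimated and may be zero. The study is descriptive, with no hypothesis test, and no decision rule in the documents uses the shift table.

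**What to change.** Limit the conversion rule in SAP 5.4.7 to descriptive statistics and add a grading rule, for example:

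> Toxicity grade is derived from the result as reported, including its sign: a result of '>x' is treated as above x and a result of '<x' as below x. The bare limit is used only for descriptive statistics. Where the reporting limit lies on the milder side of a grade cut-off, so that the grade remains uncertain, the result is flagged in the listing and the number of such results is footnoted in the shift table.

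The cost is a few sentences in the SAP and a small change to the grading program, which must read the original character result instead of the converted number. No new data are needed, and no other planned analysis changes.
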